##### **6.3.4.5. Worst-Case Abnormality**

The worst-case post-baseline categorized actual analysis value will be determined per subject, per parameter, using all non-missing post-baseline records (including unscheduled and FU visits).

##### **6.3.4.6. The worst-case categorized actual analysis value is the category corresponding to the highest post-baseline actual value. In case of several equal highest post-baseline actual values, the earliest occurrence will be taken for the analyses and will be flagged in the listings. Presentation of Results**

No formal inferential statistics (p-values) will be derived.

Continuous parameters will be summarized by means of descriptive statistics (including 90% CI of the mean change) by parameter, treatment group and analysis window. Actual values, change from baseline and percent change from baseline will be tabulated separately.

Graphs of the mean (+- SE) actual values over time and of the mean (+- SE) change from baseline, and percent changes from baseline will be presented.

The analysis of abnormalities will focus on assessments reported during the treatment period. Results reported during the screening or post-treatment (if defined) period will only be listed.

Abnormalities of the actual values will be presented as shift tables of the worst-case abnormality versus the baseline abnormality. The table will be created per parameter (and position if applicable), treatment group and analysis period.

A frequency table of the number (percent) of subjects with treatment-emergent worst-case abnormalities per parameter, treatment group and analysis period will be presented.

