### 6.3.2.7. Worst-Case Principle

#### Toxicity Grading

The worst-case post-baseline toxicity grade 0, 1, 2, 3 or 4 will be determined per subject, per laboratory test (and direction, increases and decreases) and for each analysis period, using all non-missing post-baseline records (including unscheduled and FU visits).

The worst-case toxicity grade is the highest toxicity grade corresponding to the highest laboratory test value (by direction, increases and decreases). In case of several equal highest post-baseline actual values, the earliest occurrence will be taken for the analyses and will be flagged in the listings.

- Grade 0: all post-baseline toxicity grades are classified as 0
- Grade 1: all post-baseline toxicity grades are classified as  $\leq 1$
- Grade 2: all post-baseline toxicity grades are classified as  $\leq 2$
- Grade 3: all post-baseline toxicity grades are classified as  $\leq 3$
- Grade 4: all post-baseline toxicity grades are classified as  $\leq 4$

If any record is missing, then the toxicity grade is considered as ‘missing’.

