#### Non-graded Abnormalities

The following worst-case post-baseline abnormalities L, N or H will be determined per subject, per laboratory test and for each analysis period, using all non-missing post-baseline records (including unscheduled and FU visits):

- L = low: at least one post-baseline result is classified as L.
- N = normal: all post-baseline results are classified as N.
- H = high: at least one post-baseline result is classified as H.

If, for a subject, both L and H are reported, the subject will be counted twice in the table: once with a worst-case L and once with a worst-case H.

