### **Worst-Case Abnormality**

The worst-case post-baseline categorized actual analysis value and the worst-case categorized change from baseline for QT and QTcF will be determined per subject, per parameter, and for each analysis period, using all non-missing post-baseline records (including unscheduled and FU visits).

The worst-case categorized actual analysis value is the category corresponding to the highest post-baseline actual value. In case of several equal highest post-baseline actual values, the earliest occurrence will be taken for the analyses and will be flagged in the listings.

The worst-case change from baseline is the category corresponding to the largest increase (positive change) from baseline. In case of several equal largest increase from baseline, the earliest occurrence will be taken for the analyses and will be flagged in the listings.

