##### **6.3.4.3. Abnormalities**

Vital signs data will be categorized according to the cutoffs provided in the SAP [Appendix II](#).

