##### **6.3.4.4. Treatment-Emergent Principle**

A post-baseline abnormality class L or H is defined as treatment-emergent when it differs from the abnormality class at baseline. If the baseline result is missing, a post-baseline abnormality L or H will be considered as treatment-emergent.

An abnormal category for change from baseline is always treatment-emergent.

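### Vital-sign worst case is taken from the highest value only, so low readings mostly drop out of the worst-case tables; the laboratory worst-case rule also contradicts itself on missing records

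*SAP*

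**What the plan says.** **Vital signs.** SAP 6.3.4.3 states: "Vital signs data will be categorized according to the cutoffs provided in the SAP" Appendix II. That appendix has low grades for systolic pressure (L1 below 90, L2 below 60 mmHg), diastolic pressure (L1 below 60, L2 below 45 mmHg), heart rate (L1 below 60, L2 below 50, L3 below 40 bpm) and temperature (L2 below 35 °C). Weight is graded only as a change of at least 7% from baseline, in either direction. Section 6.3.4.4 expects low classes to be reported: "A post-baseline abnormality class L or H is defined as treatment-emergent when it differs from the abnormality class at baseline". Section 6.3.4.5 sets one worst case per subject and parameter, and the sentence printed with the heading of 6.3.4.6 defines it: "The worst-case categorized actual analysis value is the category corresponding to the highest post-baseline actual value". The shift tables and the treatment-emergent frequency table in 6.3.4.6 are built on that value.

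**ECG.** Section 6.3.3.3 uses the same highest-value sentence, limited to QT and QTcF, and adds a rule for change: the "worst-case categorized change from baseline for QT and QTcF will be determined per subject, per parameter".

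**Laboratory.** Section 6.3.2.7 works by direction: "The worst-case toxicity grade is the highest toxicity grade corresponding to the highest laboratory test value (by direction, increases and decreases"). For non-graded classes, "If, for a subject, both L and H are reported, the subject will be counted twice in the table". Its toxicity-grade rule is applied "using all non-missing post-baseline records (including unscheduled and FU visits"), but its last sentence reads: "If any record is missing, then the toxicity grade is considered as" missing.

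**The concern.** The SAP sets up low vital-sign classes and then selects with a rule that can rarely return one. The highest-value rule suits QTc, which Appendix II grades only upwards. It does not suit parameters graded in both directions, and the laboratory section shows that the authors knew how to handle those.

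Safety and tolerability is a secondary objective. A drug-related tendency to intermittent low pressure or low pulse would be largely absent from the two vital-sign tables meant to count abnormalities. These tables are also the only summary of low heart rate by category, because the ECG abnormality classes cover QT and QTcF alone.

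The two laboratory sentences give different answers for any subject with one missing record. Read literally, a known grade 3 neutrophil count loses its grade in the graded tables because another sample is missing. The non-graded table would still show it as low.

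**Working it through.** The plan states no figure on this point, so there is none to reproduce. The check applies the rule as written and then sizes its effect.

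**Step 1: example readings (Appendix II cut-offs).** The heart-rate row is assumed to govern the pulse rate listed in 6.3.4.1.

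| Readings | Rule as written | By direction |
|---|---|---|
| HR 68, 45, 72, 70 | normal (72) | L2 (45) |
| HR 72, 38, 70, 68 | normal (72) | L3 (38) |
| HR 55, 48, 58, 59 | L1 (59) | L2 (48) |
| SBP 118, 58, 112, 115 | normal (118) | L2 (58) |
| SBP 84, 142, 118, 120 | H2 (142) | L1 (84) and H2 (142) |

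The maximum is low only if all readings are low. One non-low reading therefore removes the subject from the low class. This needs no assumption.

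**Step 2: share of subjects kept.** From the documents: *k* = 4 scheduled post-baseline readings for a completer (Visits 3, 4, 5 and follow-up) and 20 subjects planned on GLPG3970. Assumed, because the documents give neither: the chance *p* of a low value at each reading (5 to 20%) and the within-subject correlation *ρ*, under an exchangeable normal model cut at the *p*-quantile.

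Kept share = P(all *k* low) / P(at least one low). At *ρ* = 0 this is *p*⁴ / [1 − (1 − *p*)⁴]; otherwise it is found by numerical integration.

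| *ρ* | *p* = 5% | *p* = 10% | *p* = 20% |
|---|---|---|---|
| 0 | <0.0001 | 0.0003 | 0.0027 |
| 0.5 | 0.018 | 0.035 | 0.075 |
| 0.7 | 0.066 | 0.101 | 0.165 |
| 0.9 | 0.244 | 0.303 | 0.387 |

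For *ρ* from 0.5 to 0.9, the share lost runs from 1 − 0.387 = 61% to 1 − 0.018 = 98%.

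Example at *ρ* = 0.7 and *p* = 10%: P(any low) = 0.217 and P(all low) = 0.022. In 20 subjects, 20 × 0.217 = 4.3 are expected to have a low reading and 20 × 0.022 = 0.4 to be tabulated as low.

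With three readings (one visit missed) and *ρ* from 0.5 to 0.9, the kept share is 0.042 to 0.461.

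**Step 3: laboratory sentences.** If each of four records is independently missing with probability *m* (assumed), the literal last sentence blanks 1 − (1 − *m*)⁴ of subjects:

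- *m* = 2%: 1 − 0.98⁴ = 7.8%
- *m* = 5%: 1 − 0.95⁴ = 18.5%
- *m* = 10%: 1 − 0.90⁴ = 34.4%

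Under the all-non-missing reading, no subject with a result is blanked. SAP 4.4.3 keeps every subject with post-baseline data in the denominator, which agrees with that reading and not with the literal one.

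**The case against.** **Size.** The percentages rest on assumed inputs, and the loss of most low subjects is not universal. At *ρ* = 0.95 with *p* = 20%, 48% are lost; with three readings, *ρ* = 0.95 and *p* = 10%, 49%. That is correct. The certain statement is the narrower one in Step 1.

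**Baseline.** The example of 4.3 against 0.4 ignores the baseline class, which matters for the treatment-emergent table. Treating baseline as a fifth exchangeable reading gives about 2.8 of 20 subjects newly low, of whom about 0.1 would be shown. The count falls, but the loss remains.

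**Other outputs.** Mean change with 90% CI by window, per-window minima, mean plots, listings and TEAEs are unaffected. Clinically significant abnormal vital signs must be recorded as AEs (protocol 8.5.4). Readings that are low at every visit still appear, and no formal safety testing is planned. All of this limits the harm, but none of it corrects the two tables.

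**Laboratory.** This part is weaker. The last sentence of 6.3.2.7 may mean only that a record without a result has no grade, or that a subject with no usable record has none. An unattended visit may create no record at all. The Appendix I requirement to describe treatment-emergent abnormalities of grade 2 or above in the CSR still applies, the listings keep the value, and liver thresholds have their own table in 6.3.2.8. Even so, the milder reading is not what the text says.

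**Derivation detail.** The SAP places technical derivations in a separate document not available here. It may be more precise, but the SAP should not contradict it.

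**Conclusion.** Both parts hold. The vital-sign rule is wrong as written: it conflicts with the SAP's own low grades and low treatment-emergent class, and it departs from the SAP's own laboratory convention. Any subject with at least one non-low reading is never classed low, and a subject who is low throughout gets the mildest grade. Under the stated assumptions (four readings, 5 to 20% low per reading, correlation 0.5 to 0.9), 61 to 98% of subjects with a low reading would not be shown as low. The damage is confined to the vital-sign shift table and the treatment-emergent frequency table.

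The laboratory sentences conflict on their face. The literal reading blanks 18.5% or 34.4% of subjects at an assumed 5% or 10% of records missing; the other reading blanks none. This part is a matter of wording and the lesser of the two.

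The primary analysis, significance level and sample size are untouched. This should be fixed.

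**What to change.** 1. In SAP 6.3.4.5 and 6.3.4.6, derive the vital-sign worst case separately by direction: the lowest post-baseline value for low classes and the highest for high classes. Count a subject in both if both occur, as 6.3.2.7 does for non-graded laboratory classes.
2. In the same place, state the worst-case rule for weight change in each direction (largest decrease and largest increase). The actual-value rule does not cover it, and the vital-sign section has no counterpart to the ECG rule for change.
3. In SAP 6.3.2.7, replace the last sentence of the toxicity-grading rule with: *The worst-case grade is missing only when no post-baseline result exists.*

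The cost is two or three SAP sentences and the matching programming. No new data are needed.

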#### **6.3.5. Physical Examinations**

Physical examination results will only be listed.

#### **6.3.6. SARS-CoV-2 Infection**

Results of the SARS-CoV-2 infection test will be listed for the subjects who have at least one positive test.

#### **6.3.7. Subgroup Analyses**

No subgroup analysis is planned for this clinical study as the study sample size is too small. Thus, any subgroup of this would have small sample size to be relevant or even uninterpretable.

## 6.4. Pharmacokinetic Analysis

### 6.4.1. Available Data

Blood samples for the PK assessment of GLPG3970 should be collected on the visits specified in the Schedule of Assessments in [Section 2.5](#). Pre-dose samples not collected within 22 to 26 hours after the last drug intake, or that were taken after the drug administration at the site will be excluded from descriptive statistics and flagged in the table with appropriate footnoting. The same will be done with post-dose samples taken outside of the defined time intervals.

[figure not shown]
### 6.4.2. Presentation of Results

Descriptive statistics will be provided for GLPG3970, MTX and MTX-7-OH plasma levels at each assessment time point. Observed plasma  $C_{trough}$  for GLPG3970 will be reported in the CSR. Individual GLPG3970 plasma concentrations with descriptive statistics will be presented by time point/interval. Actual blood sampling times from the last drug intake will be listed.

For calculation of descriptive statistics of GLPG3970  $C_{trough}$  (= pre-dose concentration), the following will apply:

- for pre-dose samples not collected within 21-27 hours after the last intake prior to the visit, or collected after the intake at the visit, the corresponding concentration will be excluded from descriptive statistics and flagged in the listing with appropriate footnoting.
- pre-dose samples collected within 3 days after a missed dose will also be excluded from descriptive statistics.

[figure not shown]
## **6.6. Changes to the Planned Analyses, Not Covered by Protocol Amendments**

- As per protocol, MMRM should have been used for primary analysis [REDACTED]. However, as the data is collected only at two time points (baseline and week 6) for the primary endpoint, the MCS, an ANCOVA with a multiple imputation method to handle missing values will be used for treatment comparison as main analysis and an analysis on observed case will be performed as sensitivity analysis. [REDACTED]

## APPENDICES

### APPENDIX I: LABORATORY: TOXICITY GRADING

The following tables contain a list of safety tests with associated gradings. There may be tests in this table that are not measured in this particular study.

**Table 1**    **Gradings for Hematology Parameters**

Parameter	L1	L2	L3	L4	H1	H2	H3	H4
Hemoglobin	<LLN	<10 g/dL; <6.2 mmol/L	<8 g/dL; <4.9 mmol/L	NA	>ULN	Increase in >2 g/dL above ULN	Increase in >4 g/dL above ULN	NA
Hematocrit	<LLN	NA	NA	NA	>ULN	NA	NA	NA
Mean corpuscular volume (MCV), mean corpuscular hemoglobin (MCH), mean corpuscular hemoglobin concentration (MCHC)	<LLN	NA	NA	NA	>ULN	NA	NA	NA
Platelet count - (assuming no platelet cluster)	<LLN	<75 x 10  /L	<50 x 10  /L	<25 x 10  /L	>ULN	>600 x 10  /L	>1000 x 10  /L	NA
Leukocytes	<LLN	<3.0 x 10  /L	<2.0 x 10  /L	<1.0 x 10  /L	>ULN	>20.0 x 10  /L	>100.0 x 10  /L	NA
% Polymorphonuclear Leukocytes + Band Cells	NA	NA	NA	NA	>ULN	≥90%	>95%	NA

Parameter	L1	L2	L3	L4	H1	H2	H3	H4
Neutrophils	<LLN	<1.5 x 10  /L	<1.0 x 10  /L	<0.5 x 10  /L	NA	NA	NA	NA
Eosinophils	NA	NA	NA	NA	>ULN	>5.0 x 10  or eosinophils >5%	NA	NA
Lymphocytes	<LLN	<0.8 x 10  /L	<0.5 x 10  /L	<0.2 x 10  /L	>ULN	>4.0 x 10  /L	>20.0 x 10  /L	NA
Red blood cells	<LLN	NA	NA	NA	>ULN	NA	NA	NA

**Table 2** Gradings for Blood Chemistry Parameters

Parameter	L1	L2	L3	L4	H1	H2	H3	H4
Alanine aminotransferase (ALT)	NA	NA	NA	NA	>ULN	>3.0 x ULN	>5.0 x ULN	>8.0 x ULN
Aspartate aminotransferase (AST)	NA	NA	NA	NA	>ULN	>3.0 x ULN	>5.0 x ULN	>8.0 x ULN

Parameter	L1	L2	L3	L4	H1	H2	H3	H4
Gamma-glutamyl transferase (GGT)	NA	NA	NA	NA	>ULN	>2.5 x ULN	>5.0 x ULN	>20.0 x ULN
Alkaline Phosphatase (total)	NA	NA	NA	NA	>ULN	>2.5 x ULN	>5.0 x ULN	>20.0 x ULN
Lactate dehydrogenase (LDH)	NA	NA	NA	NA	>ULN	NA	NA	NA
Total bilirubin	NA	NA	NA	NA	>ULN	>1.5 x ULN	>3.0 x ULN	>10.0 x ULN
Amylase	NA	NA	NA	NA	>ULN	>1.5x ULN	>2.0 x ULN	>5.0 x ULN
Lipase	NA	NA	NA	NA	>ULN	>1.5x ULN	>2.0 x ULN	>5.0 x ULN
Total protein	<LLN	<5.5 g/dL	<5.0 g/dL	NA	NA	NA	NA	NA
C-reactive protein (CRP)	NA	NA	NA	NA	>5mg/L	>10mg/L	>20mg/L	>30mg/L
Activated partial thromboplastin time (APTT)	NA	NA	NA	NA	>ULN	>1.5 x ULN	>2.5 x ULN	NA
Prothrombin time (PT)	NA	NA	NA	NA	≥1.10 x ULN	≥1.25 x ULN	≥1.50 x ULN	≥3.00 x ULN
International normalized ratio (INR)	NA	NA	NA	NA	≥1.2 x Baseline	≥1.5 x Baseline	≥2.5 x Baseline	NA
Creatinine	NA	NA	NA	NA	>ULN	>1.5 x ULN	>3.0 x ULN	>6.0 x ULN
Glucose (fasting)	<LLN	<55 mg/dL; <3.0 mmol/L	<40 mg/dL; <2.2 mmol/L	<30 mg/dL; <1.7 mmol/L	>ULN	>125 mg/dL; ≥6.95 mmol/L	>250 mg/dL; ≥13.89 mmol/L	≥500 mg/dL; ≥27.75 mmol/L

Parameter	L1	L2	L3	L4	H1	H2	H3	H4
Glucose ( non-fasting )	<LLN	<55 mg/dL; <3.0 mmol/L	<40 mg/dL; <2.2 mmol/L	<30 mg/dL; <1.7 mmol/L	>ULN	>160 mg/dL; ≥8.89 mmol/ L	>250 mg/dL; ≥13.89 mmol/ L	≥500 mg/dL; ≥27.75 mmol/L
HbA1c	NA	NA	NA	NA	> 6.0 %	> 6.5 %	NA	NA
Fasting insulin	<2.6 μU/mL or 18.1 pmol/L	NA	NA	NA	>24.9 μU/m or 172.9 pmol/L	NA	NA	NA
Cholesterol	NA	NA	NA	NA	>ULN	>300 mg/dL; ≥7.75 mmol/L	>400 mg/dL ; >10.34 mmol/L	>500 mg/dL; ≥12.92 mmol/L
Low-density lipoprotein (LDL)	NA	NA	NA	NA	NA	≥160 mg/dL; ≥4.12 mmol/ L	≥190 mg/dL; ≥4.90 mmol/ L	NA
High-density lipoprotein (HDL)	NA	<40 mg/dL; <1 mmol/L	NA	NA	NA	NA	NA	NA
Triglycerides	NA	NA	NA	NA	>ULN	>300 mg/dL; ≥3.42 mmol/ L	>500 mg/dL; ≥5.7 mmol/ L	>1,000 mg/d L; ≥11.4 mmol/L
Calcium ( corrected for albumin )	<LLN	<8.0 mg/dL; <2.0 mmol/L	<7.0 mg/dL; <1.75 mmol/L	<6.0 mg/dL; <1.5 mmol/L	>ULN	>11.5 mg/dL ; >2.9 mmol/L	>12.5 mg/dL ; >3.1 mmol/L	>13.5 mg/dL ; >3.4 mmol/L

Parameter	L1	L2	L3	L4	H1	H2	H3	H4
Ionized calcium	<LLN	<1.0 mmol/L	<0.9 mmol/L	<0.8 mmol/L	>ULN	>1.5 mmol/L	>1.6 mmol/L	>1.8 mmol/L
Sodium	<LLN	<130 mEq/L; <130 mmol/L	<125 mEq/L; <125 mmol/L	<120 mEq/L; <120 mmol/L	>ULN	>150 mEq/L; >150 mmol/L	>155 mEq/L; >155 mmol/L	>160 mEq/L; >160 mmol/L
Chloride	<LLN	NA	NA	NA	>ULN	NA	NA	NA
Potassium	<LLN	NA	<3.0 mmol/L	<2.5 mmol/L	>ULN	>5.5 mmol/L	>6.0 mmol/L	>7.0 mmol/L
Phosphate	<LLN	<2.0 mg/dL; <0.65 mmol/L	<1.4 mg/dL; <0.45 mmol/L	<1.0 mg/dL; <0.32 mmol/L	>ULN	NA	NA	NA
Creatine phosphokinase (CPK)	NA	NA	NA	NA	> ULN	>2.5 x ULN	>5 x ULN	>10 x ULN
Uric acid	NA	NA	NA	NA	>ULN	≥10 mg/dL; ≥0.59 mmol/L	≥12 mg/dL; ≥0.71 mmol/L	≥15 mg/dL; ≥0.89 mmol/L
Albumin	<LLN	<30 g/L	<20 g/L	NA	NA	NA	NA	NA
eGFR (or Cr/Cl)	<LLN	<60 ml/min/ 1.73 m 	<30 ml/min/ 1.73 m 	<15 ml/min/ 1.73 m 	NA	NA	NA	NA
Blood urea nitrogen (BUN)	NA	NA	NA	NA	>ULN	>2.5 ULN	>5 ULN	>10 ULN
25-hydroxyvitamin D	< 20 ng/mL or < 50 nmol/mL	NA	NA		> 60 ng/mL or > 125 nmol/mL	NA	NA	NA

Parameter	L1	L2	L3	L4	H1	H2	H3	H4
PTH (0-20y)	<9 pg/mL or 1 pmol/L	NA	NA	NA	> 52 pg/mL or 5.5 pmol/L	NA	NA	NA
PTH (>20y)	<10 pg/mL or 1.1 pmol/L	NA	NA	NA	> 65 pg/mL or 6.9 pmol/L	NA	NA	NA
TRAP5b	<LLN	NA	NA	NA	>ULN	NA	NA	NA
P1NP	<LLN	NA	NA	NA	>ULN	NA	NA	NA
CTX Type I Collagen (20y - 51y), female	NA	NA	NA	NA	>574 pg/mL	NA	NA	NA
CTX Type I Collagen (20y - 30y) male	NA	NA	NA	NA	> 677 pg/mL	NA	NA	NA
CTX Type I Collagen (30y - 51y) male	NA	NA	NA	NA	> 685 pg/mL	NA	NA	NA
CTX Type I Collagen (> 51y) female	NA	NA	NA	NA	> 1009 pg/mL	NA	NA	NA
CTX Type I Collagen (51y - 71y) male	NA	NA	NA	NA	> 705 pg/mL	NA	NA	NA

Parameter	L1	L2	L3	L4	H1	H2	H3	H4
CTX Type I Collagen (>71y) male	NA	NA	NA	NA	> 855 pg/mL	NA	NA	NA

**Table 3** Gradings for Urine Analysis Parameters

Parameter	L1	L2	L3	L4	H1	H2	H3	H4
Urine erythrocytes	NA	NA	NA	NA	≥ULN	≥10 cells/HPF	NA	NA
Urine protein	NA	NA	NA	NA	1+ proteinuria	2+ and 3+ proteinuria; urinary protein <3.5 g/24 hrs	urinary protein ≥3.5 g/24 hrs; 4+ proteinuria	NA
Urine glucose	NA	NA	NA	NA	>ULN (presence of glucose)	NA	NA	NA

LLN: lower limit of normal, ULN: upper limit of normal, NA: not applicable.

Any laboratory parameter with treatment-emergent (i.e., worsening from baseline) abnormalities of grade 2 or above (ie, H2/L2 or higher/lower) should be considered a 'marked laboratory abnormality'. Marked laboratory abnormalities should be described in a corresponding section of the CSR as per ICH E3 guidance, section 12.4.2.3.

**APPENDIX II: Vital Signs and Electrocardiogram grading****Table 4 Gradings for Vital Signs and Electrocardiogram Parameters**

Parameter	L1	L2	L3	L4	H1	H2	H3	H4
Systolic blood pressure (mmHg)	<90	<60	NA	NA	NA	≥140	≥160	≥180
Diastolic blood pressure (mmHg)	<60	<45	NA	NA	NA	≥90	≥100	≥120
Heart rate (bpm)	<60	<50	<40	NA	>100	>115	>130	NA
Body temperature (°C)	NA	<35	NA	NA	>38	NA	NA	NA
Respiratory rate (breaths per minute)	<12	NA	NA	NA	>20	NA	NA	NA
O 2 saturation (%)	<95	<90	NA	NA	NA	NA	NA	NA
Weight	≥7% decrease from baseline	NA	NA	NA	≥7% increase from baseline	NA	NA	NA
QTc interval on ECG (ms)	NA	NA	NA	NA	>450	>480	>500	NA
QTc change from baseline (ms)	NA	NA	NA	NA	NA	>30	>60	NA
PR interval on ECG (ms)	<110	NA	NA	NA	>200	NA	NA	NA

Parameter	L1	L2	L3	L4	H1	H2	H3	H4
QRS complex on ECG (ms)	<60	NA	NA	NA	>120	NA	NA	NA

Source: FRM-MED-005/006, valid on 08JUL2020.

**APPENDIX III: Mayo Scoring System**

[figure not shown]
	0	1	2	3
Stool frequency [MCS-SF]a	Normal	1 -2 stools above normal	3 -4 stools above normal	>4 stools above normal
Rectal bleeding [MCS-RB]a	No blood seen	Streaks of blood less than half the time	Obvious blood with stool most of the time	Blood alone passed
Flexible sigmoidoscopy [MCS-ES]b	Normal or inactive disease	Mild disease (Erythema, decreased vascular pattern, no friability)	Moderate disease (Marked erythema, absent vascular pattern, friability, erosions)	Severe disease (Spontaneous bleeding, ulceration)
Physician's global assessment [PGA]a	Normal	Mild disease	Moderate disease	Severe disease

[figure not shown]
a (Lewis, et al., 2008)

[figure not shown]
b (Schroeder, Tremaine, & Ilstrup, 1987)

[figure not shown]

[figure not shown]

[figure not shown]

[figure not shown]

[figure not shown]

[figure not shown]

[figure not shown]

[figure not shown]

[figure not shown]

[figure not shown]

[figure not shown]

[figure not shown]

Signature Page for glpg3970-cl-210-sap 16159

Approval	
	16-Jun-2021 08:20:17 GMT+0000

Approval	
	16-Jun-2021 10:23:48 GMT+0000

Signature Page for glpg3970-cl-210-sap43952\_17539\_53034
